Noone et al. 2013). These findings indicate that FVIII prophylaxis delays, but does not completely prevent, long-term skeletal morbidity (Oldenburg 2015). This is in part due to the challenges of adherence and in part due to microbleeds associated with low FVIII trough levels (Ljung and Gretenkort-Andersson 2015). Due to the short half-life of FVIII, current prophylaxis regimens aim at maintaining FVIII levels at a trough of $\geq 1\%$, which restores hemostasis for only part of the time (Valentino et al. 2012). A study of patients with varying severities of hemophilia suggests that protection from joint bleeds occurs only at continuous levels over 12% (Den Uijl et al. 2011), and achieving higher FVIII activity, though difficult to accomplish with current regimens, has been recognized as a goal for optimal care in a position paper from the World Federation of Haemophilia (Skinner 2012).

Routine IV FVIII therapy relies on the venous cannulation skills of patients and their care providers (Hacker et al. 2001). In particular, this issue plagues the care of children with hemophilia, in whom central venous access devices (CVADs [i.e., Part-a-Cath®]) have been used regularly to overcome technical difficulties. Although CVADs make prophylaxis feasible in young children, they are associated with complications, including mechanical failure, dehiscence of the skin over the reservoir, infection, and thrombosis (Ewenstein et al. 2004). A recent prospective study reported that 183 lines were implanted in 99 patients and that 41% of patients had at least one infectious episode. The median time to line removal was 483 days (interquartile range: 143–1071; Rodriguez et al. 2015). A Finnish retrospective study similarly reported that 47% of 106 catheters implanted in 58 patients had to be removed due to a complication (Vepsalainen et al. 2015). In addition, significant health care provider efforts are required to manage optimal treatment solutions and to overcome identified issues (Schrijvers et al. 2013). Thus, both the disease and its treatment affect patients' health-related quality of life (HRQoL).

The development of inhibitory alloantibodies (inhibitors) occurs in approximately 20%–30% of patients with severe hemophilia A and in 3%–13% of those with moderate or mild disease (Franchini and Mannucci 2013). In China, the development of inhibitors occurs in approximately 9%–15% of patients with hemophilia A. Because inhibitors can develop very early during the course of FVIII therapy (within 10–50 exposure days), with half of all cases occurring before the age of 5 years, pediatric patients represent the population at highest risk of developing inhibitors (Kreuz et al. 1995; Wight and Paisley 2003; Kempton and White 2009; Hay and DiMichele 2012). Inhibitors neutralize the activity of endogenous FVIII as well as of FVIII administered as replacement therapy.

For patients who develop inhibitors against FVIII, immune tolerance induction (ITI) may help restore a patient's clinical response to FVIII concentrates. Permanent eradication of FVIII inhibitors is the ultimate goal of ITI, and it is successful in approximately 60%–80% of adults and children with inhibitors (Santagostino et al. 2009; Hay and DiMichele 2012). Most physicians delay the start of ITI for up to 1 year from the time the inhibitor is first diagnosed to allow very high titers of inhibitors to fall because a pre-ITI

inhibitor titer measuring <10 BU/mL is the most powerful predictor of ITI success (Mariani and Kröner 1999; DiMichele and Kröner 2002). Regimens that delay treatment until the inhibitor has fallen below 10 BU/mL positively affect both the likelihood of success (79%–87% success rate) and the time required to achieve tolerance (Mauser-Bunschoten et al. 1995; Kröner 1999; Rocino and de Biasi 1999; Smith et al. 1999). Furthermore, the rate of response to ITI does not decline until ITI has been delayed beyond 5 years from the time of diagnosis (Brackmann et al. 1996; Mauser-Bunschoten et al. 1995; Kröner 1999; DiMichele and Kröner 2002). However, an optimal regimen for ITI remains to be defined (although a recent study suggested superior safety outcomes using high-dose regimens administered daily [Hay and DiMichele 2012]), and the length of treatment is dictated by individual responses, ranging from months to years. Because uninterrupted and uncomplicated venous access is essential in children undergoing ITI, this process is particularly burdensome in the pediatric patient population, who require frequent visits to hemophilia centers for regular infusion of FVIII concentrate through CVADs.

Long-term CVAD use requires considerable commitment from caregivers and patients, and serious complications can occur, including thrombosis, bleeding, mechanical dysfunction, and most commonly, infection. A prospective study in pediatric hemophilia A patients with inhibitors reported that 183 lines were implanted in 99 patients, with 41% of patients having at least one documented infection. The median time to line removal was 483 days [interquartile range (143–1071; Rodriguez et al. 2015)]. A Finnish retrospective study similarly reported that 47% of 106 catheters implanted in 58 patients had to be removed because of a complication (Vepsäläinen et al. 2015). CVAD-related bacteremia and sepsis pose potentially lethal problems for patients with hemophilia and result in a substantial proportion of emergency room visits for children. A retrospective study of pediatric emergency department management of children with hemophilia showed that of 536 visits from 84 male patients (median age 4 years), 12% were due to suspected CVAD infection (Ozgonenel et al. 2013). Indeed, infection occurs more frequently in hemophilia patients with inhibitors (Bolland et al. 2000; Valentino et al. 2004; van Dijk et al. 2004), with rates being highest among patients with inhibitors undergoing ITI, ranging from 50%–83% (van den Berg et al. 1998). If ITI is unsuccessful, inhibition of FVIII concentrate treatment may persist throughout the patient's life. Additionally, the use of ITI treatment is not viewed as a viable option for patient management in many countries, owing to its high cost, lack of availability of FVIII concentrates, and daily administrations. These disadvantages are compounded in the young pediatric population due to the necessity for central venous access and related complications, as well as the psychological stress of this treatment on patients and their families.

For patients with a history of a high-titer (≥ 5 BU/mL) inhibitor who are unable to eradicate their inhibitors or are not candidates for ITI, the only hemostatic options currently available are prothrombotic coagulation factors that augment other parts of the

coagulation cascade (i.e., “bypassing agents”). Bypassing products include factor eight inhibitor bypassing activity (FEIBA), an activated prothrombin complex concentrate (aPCC; FEIBA will be henceforth referred to as aPCC), and NovoSeven® (recombinant activated human FVIIa [rFVIIa]; NovoSeven® will be henceforth referred to as rFVIIa; Srivastava et al. 2013). Unfortunately, the hemostatic effect of bypassing agents in patients with inhibitors is suboptimal, leading to a higher number of bleeds (annualized bleeding rate [ABR] of 8–10 with FEIBA [Leissinger et al. 2011; Antunes et al. 2014] and 2–3 bleeds per month with NovoSeven [Konkle et al. 2007] compared with that of FVIII concentrates in non-inhibitor patients who achieve a median ABR of approximately 0–2 with optimal prophylaxis (Manco-Johnson et al. 2013). In China, the available products are prothrombin complex concentrate (PCC) and rFVIIa; however, due to the high cost of the prophylaxis treatment, the majority of the patients with inhibitors can only afford on-demand treatment when there are bleeds, thus causing suboptimal bleeding control compared to those patients with prophylaxis treatment. In addition, as opposed to the 8- to 12-hour half-life and 15- to 20-minute infusion time of FVIII, NovoSeven® has a short half-life of only 2–3 hours, and FEIBA requires 25–50 minutes to infuse (with a half-life of 4–7 hours), requiring frequent and extended IV infusions, respectively.

Investigations into prophylactic therapy in adults and children with bypassing agents NovoSeven® (Konkle et al. 2007) and FEIBA (Leissinger et al. 2011; Antunes et al. 2014) have shown that these products lead to reductions in bleed rates compared with episodic treatment with these same products. However, as detailed above, this efficacy is suboptimal and does not approach the level of hemophilia control that can be achieved with FVIII concentrates in non-inhibitor patients.

Despite prophylactic regimens being standard-of-care for hemophilia patients without inhibitors in many countries, a large proportion of hemophilia patients with FVIII inhibitors currently are treated with episodic regimens, partly because of the treatment burden of these prophylaxis regimens. A survey of hemophilia centers across 14 countries suggested that 41% of pediatric hemophilia patients with inhibitors were on ITI alone, 17% were on both ITI and prophylactic bypassing agents, 16% were on prophylactic bypassing agents alone, and 26% were on neither ITI nor prophylactic bypassing agents (Carcao et al. 2015).

Of note, treatment of patients with congenital hemophilia A of any severity with high-titer inhibitors is similar, and their endogenous severity, as defined based on FVIII activity at diagnosis (mild, moderate, or severe), is no longer prognostic of their clinical phenotype and risk of bleeding. This is because the inhibitor would eventually neutralize the residual endogenous FVIII, resulting in a severe bleeding phenotype in the end.

Both aPCC/PCC and rFVIIa are administered intravenously, with aPCC/PCC prophylaxis requiring every-other-day dosing and rFVIIa requiring daily (or more frequent) dosing. For years, the suboptimal bleeding control, the short half-life, and high cost of these

bypassing agents limit the use of prophylaxis treatment in inhibitor patients. Despite physician's efforts, joint disease ultimately occur.

The development of effective prophylactic treatment options with decreased immunogenicity and less frequent dosing requirements is important to reduce the time and burden associated with frequent IV dosing and the effect of the disease on aspects of physical health and other areas of function. A study assessing the relationship between self-reported adherence to prophylaxis and health outcomes (HRQoL and bleeding episodes) showed that poorer adherence with prophylaxis was associated with a greater number of self-reported bleeding episodes, more days of work or school missed among pediatric patients, and lower physical health status scores among pediatric patients (Krishnan et al. 2015). Adherence to prophylaxis by patients with hemophilia A, defined as the extent to which a person's behavior corresponds to agreed recommendations by a healthcare provider (WHO 2003), ranges from 44% to 87% (Llewellyn et al. 2003; De Moerloose et al. 2008; Ho et al. 2014). In China, the adherence to prophylaxis by patients with hemophilia A is even worse, ranging from 5% to 15% for patients without FVIII inhibitors, and almost no patients with FVIII inhibitors receive prophylactic treatment (Xue et al. 2011; Xuan et al. 2014). In a Dutch study investigating patient behavior affecting adherence to prophylactic treatment, patients were asked about their experience with and adherence to administration of prophylaxis. Remarkably, some patients willingly chose non-adherence because they did not want to adapt their activities to hemophilia, and they were prepared to accept the consequences of their decision. Patients noted the difficulties of regular prophylaxis due to inadequate routine and the complexity of the needed self-management skills including planning, management of the treatment of bleeds, forgetfulness, stock management, and overruling activities in life (Schrijvers et al. 2015).

Given the incomplete efficacy and the significant management challenges in adults and children with hemophilia, there is a true need for therapeutics that have reliable efficacy, a long half-life, low treatment burden, and ease of administration to prevent bleeding in and minimize long-term morbidity of individuals with hemophilia A.

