- ≥ 2 spontaneous and clinically significant bleeds in the last 24 weeks on emicizumab, both of which occur after the end of the loading dose period
- At least one of the bleeds must be verified by a physician (e.g., with diagnostic imaging, photograph)

Patients in Arm D will receive 3 mg/kg QW for 4 weeks as loading doses, followed by 1.5 mg/kg QW as maintenance during the 24-week treatment period. Individual patients experiencing suboptimal bleeding control on emicizumab may also have their dose up-titrated if they meet the same criteria as required for patients in Arm A, B and C and after consulting with the Medical Monitor.

NON-INVESTIGATIONAL MEDICINAL PRODUCTS

Concomitant use of the following drugs and therapies will be permitted:

- Drugs intended to control bleeds, including FVIII products or bypassing agents as standard-of-care episodic treatment. Exact dosages will not be specified in the study but rather these agents should be administered according to the respective prescribing information or as previously used by each individual patient (for information on the formulation, packaging, and handling of FVIII or bypassing agents, refer to local prescribing information for the agent in question).
- Drugs and therapies to treat adverse events and use of topical antiseptics, anesthetics, eye drops, etc., that are not considered to result in systemic exposure
- Drugs to treat an existing medical condition ongoing at study entry that do not violate the eligibility criteria (e.g., anti-retroviral therapy for HIV infections)
- Local anesthetic cream for emicizumab SC administration
- Vaccinations should be administered following national immunization schedules. As per the World Federation of Hemophilia recommendations for vaccinations (World Federation of Hemophilia 2012), patients with hemophilia should be vaccinated. Thus, vaccinations should be administered according to the World Federation of Hemophilia recommendations and local Hemophilia Treating Center practice and ideally during a period when the bleeding status of the child is well controlled and stable. Vaccinations should not be administered on the same day as an emicizumab administration but ideally at a timepoint between two emicizumab administrations (>48 hours after emicizumab administration). Children who receive vaccinations must be carefully followed for any adverse reactions in the subsequent days following vaccine administration.

STATISTICAL METHODS

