However, in the ongoing Phase III Study BH29884 (adolescent and adult patients with hemophilia A with FVIII inhibitors), three thrombotic microangiopathy and three thromboembolic events were observed in 5 patients on emicizumab who concomitantly used on average, cumulative doses of >100 units/kg/24 hr for 24 hours of aPCC for the treatment of breakthrough bleeds. There was an additional thromboembolic event, which was a device occlusion without concomitant aPCC and assessed by the investigator as being unrelated to emicizumab (see [Section 1.2](#), [Section 1.3](#), [Section 5.1.2.1](#), and [Section 5.1.3](#)). Although FVIII and aPCC are fundamentally different in their potential interaction with emicizumab, investigators should keep in mind

that circulating emicizumab increases patients' coagulation potential. Therefore, it is recommended that:

- Breakthrough bleeds should be treated with the lowest FVIII or rFVIIa dose expected to achieve hemostasis, which may be lower than the patients' prior dose. Investigators should review with patients the dose to be used to treat breakthrough bleeds.
- The use of aPCC/PCC or other bypassing agents should be avoided or limited (see Section 4.4.1).
- Investigators and patients should consider objective verification of bleeds.

Also, local laboratory assessments are required to monitor the risk for thromboembolic events or thrombotic microangiopathy as per the schedule of assessments (see Section 4.5.5 and [Appendix 1-A](#)).

Patients might require dosing with FVIII or bypassing agents for the treatment of potential breakthrough bleeds, especially for the time period until steady-state concentrations of emicizum

ab have been reached. The reason for the use of coagulation products will be documented (e.g., bleeding, prophylaxis). The number of infusions needed to treat the bleed will be derived from the medication log.

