4.4.1 Permitted Therapy

Concomitant use of the following drugs and therapies will be permitted:

- Drugs intended to control bleeds, including FVIII products or bypassing agents as standard-of-care episodic treatment. Exact dosages will not be specified in the study; however, investigators should consider that circulating emicizumab may increase patients' coagulation potential. Investigators should review with patients the dose to be used to treat breakthrough bleeds. Breakthrough bleeds should be treated with the lowest FVIII or rFVIIa dose expected to achieve hemostasis, which may be lower than the patients' prior FVIII or rFVIIa dose.

Caution should be taken for patients who are using rFVIIa (e.g., consideration of using no more than 90 µg/kg of rFVIIa as an initial dose).

Use of aPCC/PCC in combination with emicizumab should be avoided completely in patients who have the option of using other bypassing agents to treat bleeds. In the event that aPCC/PCC is the only available bypassing agent, the lowest dose expected to achieve hemostasis should be prescribed, with no more than 50 units/kg of aPCC/PCC to be administered as an initial dose.

Other bypassing agents (e.g., Byclot[®]) should be avoided. In cases where such agents are the only available bypassing agent, the lowest dose expected to achieve hemostasis should be prescribed, with no more than the lowest dose described in the prescribing information to be administered as an initial dose (e.g., no more than 60 µg/kg of Byclot[®]).

Exact dose and schedule of bypassing agents should be discussed with patients at the beginning and throughout the study. Repeated dosing of rFVIIa, aPCC/PCC, or other bypassing agents should be performed only under medical supervision, which includes laboratory monitoring by additional local laboratory assessments (see [Appendix 1-A](#)), and consideration should be given to verifying bleeds prior to repeated dosing.

Caution should be taken if anti-fibrinolitics are used in conjunction with rFVIIa in patients receiving emicizumab.

- Drugs and therapies to treat adverse events and use of topical antiseptics, anesthetics, eye drops, etc., that are not considered to result in systemic exposure
- Drugs to treat an existing medical condition ongoing at study entry that do not violate the eligibility criteria (e.g., anti-retroviral therapy for HIV infections)
- Local anesthetic cream for emicizumab SC administration

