5.1.2 Risks Associated with Emicizumab

5.1.2.1 Identified Risks

Thrombotic Microangiopathy (Associated with Emicizumab and aPCC)

Thrombotic microangiopathy is a very rare, but serious condition whereby microvascular thrombosis leads to organ damage.

As of October 2018, among 417 patients in five studies (ACE002JP, BH29884, BH29992, BH30071, and BO39182), there were 3 patients (1.0%), all in Study BH29884, who experienced thrombotic microangiopathy while receiving emicizumab prophylaxis. These events are believed to be caused by an interaction between emicizumab and aPCC, as all 3 patients received cumulative doses of >100 U/kg/day on average of aPCC for ≥24 hours for the treatment of breakthrough bleeds just prior to developing symptoms. These events were reported as serious adverse events (two Grade 4 events and one Grade 3 event). One patient died due to a serious adverse event of Grade 4 rectal haemorrhage (assessed as unrelated to emicizumab). From additional analyses, including data on the thrombotic microangiopathy and thromboembolic events,

there is evidence to support a drug-drug interaction between aPCC and emicizumab. Please see the Emicizumab Investigator's Brochure for a complete summary of safety information.

Specific guidance regarding the use of bypassing agents in combination with emicizumab is detailed in Section 4.4.1.

Any thrombotic microangiopathy event should be reported as an adverse event of special interest and also as a serious adverse event, if it meets criteria for such (see Section 5.2.2 and Section 5.2.3).

Guidelines for management of patients who develop thrombotic microangiopathy are provided in Section 5.1.3.

Hypercoagulation and Risk of Thrombosis

As of October 2018, four thromboembolic events have been reported in 3 patients with hemophilia A with inhibitors while receiving emicizumab in Study BH29884.

Two patients who administered cumulative doses of > 100 U/kg/day on average of aPCC for ≥24 hours while receiving emicizumab developed thromboembolic events. The thromboembolic events were reported as serious adverse events (Grade 3 cavernous sinus thrombosis, Grade 3 skin necrosis, and Grade 2 thrombophlebitis superficial); however, none were life-threatening or fatal. No anticoagulation was started and symptoms in both patients improved with supportive care. These adverse events are believed to be caused by a drug-drug interaction between emicizumab and aPCC.

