Appendix 8 (cont.): WHO Toxicity Grading Scale for Determining the Severity of Adverse Events

OTHER PARAMETERS (continued)				
Local Reaction	tenderness or erythema	induration < 10 cm or phlebitis or inflammation	induration > 10 cm or ulceration	necrosis
Mucocutaneous	erythema; pruritus	diffuse, maculo-papular rash, dry desquamation	vesiculation, moist desquamation, or ulceration	exfoliative dermatitis, mucous membrane involvement or erythema, multiforme or suspected Stevens- Johnson or necrosis requiring surgery

Appendix 9

Guidelines for Dosing and Monitoring Bypassing Agents for Patients on Emicizumab

The use of bypassing agents is not expected in hemophilia A patients without inhibitors. For completeness, this appendix includes guidelines provided for treatment of breakthrough bleeds in patients with inhibitors. Careful consideration of the risks and potential benefits is advised when combining emicizumab, factor VIII (FVIII), and bypassing agent.

Drugs intended to control bleeds, including bypassing agents, should be used at the lowest dose expected to achieve hemostasis. Given that circulating emicizumab may increase patients' coagulation potential, the doses required to achieve hemostasis may be lower than the FVIII or bypassing agent doses used prior to starting the study.

Caution should be taken for patients who are using recombinant activated factor VII (rFVIIa [e.g., consideration of using no more than 90 µg/kg of rFVIIa as an initial dose]).

Use of activated prothrombin complex concentrate (aPCC) or PCC in combination with emicizumab should be avoided completely in patients who have the option of using other bypassing agents to treat bleeds. In the event that aPCC/PCC is the only available bypassing agent, the lowest dose expected to achieve hemostasis should be prescribed, with no more than 50 units/kg of aPCC/PCC to be administered as an initial dose.

Other bypassing agents (e.g., Byclot®) should be avoided. In cases where such agents are the only available bypassing agent, the lowest dose expected to achieve hemostasis should be prescribed, with no more than the lowest dose described in the prescribing information to be administered as an initial dose (e.g., no more than 60 µg/kg of Byclot®).

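### The synopsis lets bleeds be dosed as before the study, without the dose limits that Section 4.4.1 and Appendix 9 set for patients on emicizumab

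*Protocol*

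**What the plan says.** The Synopsis, under Non-Investigational Medicinal Products, permits FVIII products and bypassing agents to control bleeds and leaves exact doses open. It then gives the basis for dosing: "these agents should be administered according to the respective prescribing information or as previously used by each individual patient". The bullet treats patients on emicizumab and controls alike. No part of the synopsis mentions aPCC/PCC, a dose cap or the lowest effective dose.

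The body of the protocol is narrower for patients on emicizumab:

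- **Section 4.4.1, FVIII and rFVIIa.** Use the lowest dose expected to work, which may be below the patient's earlier dose. For rFVIIa, investigators are asked to consider an initial dose of at most 90 µg/kg.
- **Section 4.4.1, aPCC/PCC.** "Use of aPCC/PCC in combination with emicizumab should be avoided completely in patients who have the option of using other bypassing agents". Where it is the only bypassing agent available, the lowest effective dose applies, "with no more than 50 units/kg of aPCC/PCC to be administered as an initial dose".
- **Section 4.4.1, repeat doses.** "Repeated dosing of rFVIIa, aPCC/PCC, or other bypassing agents should be performed only under medical supervision, which includes laboratory monitoring".
- **Section 3.1.** "The use of aPCC/PCC or other bypassing agents should be avoided or limited", with a pointer to Section 4.4.1.
- **Appendix 9.** The lowest-dose rule covers bleed treatments generally, including bypassing agents, because "the doses required to achieve hemostasis may be lower than the FVIII or bypassing agent doses used prior to starting the study". The aPCC/PCC avoidance rule and the 50 units/kg cap are repeated.

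**The concern.** The protocol gives two bases for the same decision. In the synopsis, what the patient took before is enough to justify the dose. In Section 4.4.1 and Appendix 9, the previous dose is something that may need to come down once emicizumab is circulating.

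The limits in the body exist because of an identified risk. On thrombotic microangiopathy under emicizumab, Section 5.1.2.1 records that "all 3 patients received cumulative doses of >100 U/kg/day on average of aPCC" for at least 24 hours just before symptoms. It also cites evidence of an interaction between the two drugs. A written dosing permission that is looser than the control for that risk should not stand in the current protocol.

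**Working it through.** There is no figure to reproduce. The check sets the synopsis clause beside the body, case by case, and asks whether conduct that satisfies the synopsis could breach Section 4.4.1 or Appendix 9.

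1. **On emicizumab, bleed treated with FVIII or rFVIIa at the pre-study dose, when a lower dose is expected to work.** The synopsis allows it. Sections 3.1, 3.3.3 and 4.4.1 and Appendix 9 call for the lower dose. This is a conflict.
2. **On emicizumab, aPCC/PCC the only agent available, earlier initial dose above 50 units/kg.** The synopsis allows the earlier dose to be repeated. Section 4.4.1 and Appendix 9 do not. This is a conflict, and the one with a numerical limit.
3. **As in case 2, but earlier initial dose at or below 50 units/kg.** The cap is met. The texts differ only if a lower dose is expected to work.
4. **On emicizumab, aPCC/PCC used before, another bypassing agent now an option.** Section 4.4.1 and Appendix 9 say to avoid aPCC/PCC. The synopsis clause is about dose and does not tell sites to keep the earlier agent. A site that chooses rFVIIa breaches neither text on choice of agent. This is an omission, not a contradiction.
5. **On emicizumab, repeat bypassing-agent doses.** Section 4.4.1 requires medical supervision with laboratory monitoring. The synopsis does not mention repeat doses. This too is an omission.
6. **Arm C before the switch.** The lowest-dose rule and the cap rest on circulating emicizumab, which these patients do not have. The synopsis clause suits them, and there is no conflict.

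The conflict is therefore confined to cases 1 and 2, and to case 3 where a lower dose is expected to suffice.

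The wording looks like text that was not updated. SAP Appendix 1 reproduces the synopsis of protocol version 3, which has the same sentence. The current synopsis adds bullets on anesthetic cream and vaccinations to the same list, in line with Section 4.4.1, but leaves the bleed-treatment bullet as it was. This is an inference about origin, and the finding does not depend on it.

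**The case against.** The strongest case on the other side is that this is only a summary, and that the body is clear and consistent. Sections 3.1 and 4.4.1 and Appendix 9 agree with each other. Section 3.3.3 has investigators approve the breakthrough dose of FVIII or rFVIIa. Section 4.5.5 and the bypassing-agent footnote in Appendix 1-A set laboratory checks within 24–48 hours of first bypassing-agent use and every 24–48 hours while doses continue, and Section 3.1 calls local laboratory monitoring required. Section 4.3.2 has the investigator contact the Medical Monitor at once when an unanticipated event needs multiple daily doses. The synopsis waives none of this.

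Most of that stands, and it rules out several stronger readings that a reader might infer:

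- **That the synopsis sets no limit at all.** It names prescribing information as one of its two standards. The labels are not in the documents, so only the absence of an emicizumab-specific limit can be asserted.
- **That it overrides the rule on avoiding aPCC/PCC, or permits unsupervised repeat dosing.** It is silent on both, and silence in a summary is not permission.
- **That a safeguard is missing.** The rule and the monitoring are in the body. In the extension phase, Appendix 1-B words the monitoring as a recommendation, but that is separate from the synopsis clause.
- **That the size can be read from the number of inhibitor patients on emicizumab, or from multiples of the 50 units/kg cap.** The first counts patients in scope, not patients affected. The second describes repeat dosing that Section 4.4.1 itself leaves open under supervision, since the cap covers the initial dose only.

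The link to harm is also indirect. The microangiopathy events followed sustained aPCC, and Section 5.1.2.1 reports no thromboembolic events with single aPCC doses up to 100 U/kg. Section 1.1.1 lists PCC and rFVIIa as the products available in China, where most patients are enrolled. The body does, however, apply the same restriction to PCC.

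The objection does not reach the dose clause itself. A summary may leave detail out, but this one states a dosing basis that the body does not accept for patients on emicizumab.

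**Conclusion.** The point holds as a minor inconsistency in safety text. For patients on emicizumab, the synopsis accepts the pre-study dose as a sufficient basis. Section 4.4.1 and Appendix 9 call for the lowest effective dose and cap the initial aPCC/PCC dose at 50 units/kg when no other bypassing agent is available.

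The number of patients affected cannot be derived. The documents do not give each patient's earlier agent and dose, access to an alternative, or the breakthrough bleeds to come. Any harm assumes a site that doses from the synopsis without reading Section 4.4.1. Confidence is high on the mismatch in wording. The documents do not show that it has changed anyone's treatment. The primary analysis and sample size are unaffected.

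**What to change.** At the next amendment, limit the prior-use clause in the synopsis bullet to Arm C before the switch. For patients on emicizumab, put one of these in its place:

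- the Section 4.4.1 rule in short form: lowest dose expected to work, possibly below the pre-study dose; aPCC/PCC avoided when another bypassing agent is an option, otherwise at most 50 units/kg initially; repeat bypassing-agent doses only under medical supervision with laboratory monitoring; or
- an explicit cross-reference to Section 4.4.1 and Appendix 9.

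The cost is one clause. The SAP needs no change for this, because its Appendix 1 is labelled as the version 3 synopsis.
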